9.11. Long-term Follow-up Phase

Medtronic Business Restricted

Once subjects complete the aDBS Evaluation Phase (one or two evaluation visits), they enter a Long-term Follow-up Phase. During this Phase, the investigator may choose to switch aDBS modes as needed, so long as the subject received both modes during the aDBS Evaluation Phase. Any changes to the aDBS mode must be done at a study visit, either scheduled or unscheduled.

Prior to each scheduled long-term follow-up visit (visit #3 through #6 inclusive), the PKG Watch will be given to the subject or mailed to the subject's home. Upon receipt, the subject will put on and activate the PKG Watch. The PKG Watch will be worn on the most affected side for at least 6 consecutive days in the 14 days prior to each visit. After the recording, the subject will return the PKG Watch in the pre-paid mailer or bring it to the site for return at the visit.

The PDQ-39 and EQ-5D-5L may be completed prior to each scheduled visit. See Section [9.15](#) for detailed information about the administration of each assessment.

In the Long-term Follow-up Phase, subjects may choose to participate in optional data collection of Events with LFP capture (snapshots). The clinician may set up a maximum of 4 event types, selected from the following options: *dyskinesia, tremor, rigidity, freezing, sleep disturbance, took PD medication*. Study personnel will instruct the subject on how to record each event type utilizing the Patient Programmer System.

9.11.1. Visit 3

45-60 days after Evaluation Visit 2 (or Evaluation Visit 1 if the subject is only configured to one aDBS mode)

The subject will arrive for the visit on their preferred aDBS mode.

Data collection:

- Concomitant medications
- PDQ-39
- EQ-5D-5L
- Collect PKG Watch or confirm it was returned via mail
- Programming session upload to Medtronic via CDU, with BrainSense data included in the JSON session data report
- Adverse Event and device deficiency assessment

The subject should be reminded that they will receive the PKG Watch prior to the next visit and will put on and activate the PKG Watch upon receipt. The subject will wear the PKG Watch on the most affected side for at least 6 consecutive days in the 14 days prior to the scheduled visit. The subject will return the PKG Watch in the pre-paid mailer or bring it to the site for return at Visit 4.

Medtronic Business Restricted

9.11.2. Visit 4

45-60 days after Visit 3

The subject will arrive for the visit on their preferred aDBS mode.

Data collection:

- Concomitant medications
- PDQ-39
- EQ-5D-5L
- Collect PKG Watch or confirm it was returned via mail
- Programming session upload to Medtronic, with BrainSense data included in the JSON session data report
- Adverse Event and device deficiency assessment

The subject should be reminded that they will receive the PKG Watch prior to the next visit and will put on and activate the device upon receipt. The subject will wear the PKG Watch on the most affected side for at least 6 consecutive days in the 14 days prior to the scheduled visit. The subject will return the PKG Watch in the pre-paid mailer or bring it to the site for return at Visit 5.

9.11.3. Visit 5

90 +/- 14 days after Visit 4

The subject will arrive for the visit on their preferred aDBS mode.

Data collection:

- Concomitant medications
- PDQ-39
- EQ-5D-5L
- Collect PKG Watch or confirm it was returned via mail
- Programming session upload to Medtronic via CDU, with BrainSense data included in the JSON session data report
- Adverse Event and device deficiency assessment

The subject should be reminded that they will receive the PKG Watch prior to the next visit and will put on and activate the device upon receipt. The subject will wear the PKG Watch on the most affected side for at least 6 consecutive days in the 14 days prior to the scheduled visit. The subject will return the PKG Watch in the pre-paid mailer or bring it to the site for return at Visit 6.

9.11.4. Visit 6

90 +/- 14 days after Visit 5

Data collection:

- Concomitant medications

Medtronic Business Restricted

- PDQ-39
- EQ-5D-5L
- Patient satisfaction questionnaire
- Collect PKG Watch or confirm it was returned via mail
- Programming session upload to Medtronic via CDU, with BrainSense data included in the JSON session data report
- Adverse Event and device deficiency assessment

At the completion of this visit, if aDBS is not commercially approved, the subject may choose to continue participation in the study as described in [Section 9.12](#). If the subject chooses to exit the study after this visit and before aDBS is commercially approved, aDBS will be turned off as directed in [Section 9.19](#).

9.12. Extended Access Phase

Following the final long-term follow-up visit (Visit 6), subjects will be allowed extended access to aDBS through aDBS is commercially approved in the geography in which the subject is enrolled. The subject will continue the study in aDBS and return for a visit every 6 months or until aDBS is commercially approved or closure of the study, whichever comes sooner.

9.12.1. Extended Access Visits

Every 180 +/- 60 days beginning after Visit 6 and every 6 months thereafter following the previous extended access visit

Data collection:

- Concomitant medications
- PDQ-39
- EQ-5D-5L
- Programming session upload to Medtronic, with BrainSense data included in the JSON session data report
- Adverse Event and device deficiency assessment

9.13. Unscheduled Visit

Any time the subject has a visit (in person, by telephone and/or telehealth/video consult) for aDBS programming adjustment/optimization (including resuming aDBS if it was unintentionally turned off) or for an Adverse Event, the following data will be collected:

- Reason for the visit
- Concomitant medications
- Programming session upload to Medtronic via CDU, with BrainSense data included in the JSON session data report (if applicable)
- Adverse Event and device deficiency assessment

Medtronic Business Restricted

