9.2. Data Collection

Data collection requirements are summarized in [Table 3](#) below.

Table 3: Study Procedures and Data Collection by Visit

Phase Name		cDBS Baseline Phase		aDBS Setup and Adjustment Phase		aDBS Evaluation Phase		Long-term Follow-up Phase				Extended Access Phase			
Visit Name	Enrollment	LFP Screening	cDBS Baseline	aDBS Setup	Randomization	Visit 1	Visit 2*	Visit 3	Visit 4	Visit 5	Visit 6	Extended Access Visits	Subject Withdrawal / Discontinuation	Unsched. Visit	System Mod.
Informed Consent	X														
Demographics	X														
Medical & surgical history	X														
PD history	X														
C-SSRS (screening)	X														
BDI-II	X														
Pregnancy test	X														
Device information	X														X
Signal Test	X	X		X											
Concomitant medication	X	X	X	X	X	X	X	X	X	X	X	X		X	X
PD medication at visit				X											
PD medication prior to visit		X		X											
PDQ-39			X			X	X	X	X	X	X	X			
EQ-5D-5L			X			X	X	X	X	X	X	X			
MDS-UPDRS IA			X			X	X								
MDS-UPDRS Patient Questionnaire (Part IB & II) Worst condition		X				X	X								

Medtronic Business Restricted

ADAPT-PD MDT19001 Clinical Investigation Plan

Version 5.0

Page 54 of 152

Medtronic

Phase Name		cDBS Baseline Phase		aDBS Setup and Adjustment Phase		aDBS Evaluation Phase		Long-term Follow-up Phase				Extended Access Phase			
Visit Name	Enrollment	LFP Screening	cDBS Baseline	aDBS Setup	Randomization	Visit 1	Visit 2*	Visit 3	Visit 4	Visit 5	Visit 6	Extended Access Visits	Subject Withdrawal / Discontinuation	Unsched. Visit	System Mod.
MDS-UPDRS Patient Questionnaire (Part IB & II) Best condition			X			X	X								
MDS-UPDRS III On stim (cDBS) / On med			X												
MDS-UPDRS III Off stim (cDBS) / Off med		X													
MDS-UPDRS III On stim (aDBS) / On med						X	X								
MDS-UPDRS IV			X			X	X								
PD Home Diary			X			X	X								
C-SSRS (follow-up)						X	X								
VHI Worst condition			X			X	X								
VHI Best condition			X			X	X								
PDSS-2			X			X	X								
BrainSense setup		X		X											
aDBS programming				X									X**		
Physician programming survey				X**										X**	
Patient preference questionnaire						X	X								

Medtronic Business Restricted

This document is electronically controlled

CONFIDENTIAL

056-F275E Rev E Clinical Investigation Plan Template

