9.7.1. Enrollment

Subjects who have a complete Medtronic DBS system, including Percept PC, leads and extensions and whose cDBS parameters and PD medications are stable may be approached to participate in the study. From enrollment to the end of the aDBS Evaluation Period, the investigator should make only clinically necessary changes to cDBS settings.

A subject is considered enrolled when the consent process has been fully executed. The date the subject signed the IC and Data Protection Authorization, as required by law, must be documented in the subject's medical records. A log of all subjects enrolled in the study will be maintained. Once consent is obtained, report adverse events/deaths, study deviations and subject exits as they occur.

The study-specific IC will be signed and dated prior to completion of any study-related procedures. Enrolled subjects who do not meet all inclusion criteria or who meet any exclusion criteria will be discontinued from the study. No further study-related procedures will be completed, and subjects will be followed according to the center's standard procedures.

The subject will arrive for the visit with PD medications and cDBS according to the center's standard procedures. After consent, the clinician will perform a Signal Test, using a commercially available Clinician Programmer System, to ensure the subject has adequate signal quality. The clinician should ensure the subject movement is minimized during this test.

If signal artifact is detected on all six aDBS sense pathways (3 each on both DBS leads), the Signal Test may be repeated. If signal artifact is persistent on all six aDBS sense pathways, the clinician should determine whether this precludes them from setting thresholds. If not, the subject can continue in the study. If the subject will not continue, device identification information will be collected, the programming session, with BrainSense data included in the JSON session data report, will be uploaded to Medtronic via CDU, and an AE and device deficiency assessment will be performed. The subject will then be discontinued from the study, and no further study-related procedures will be completed.

Following the Signal Test, data will be collected and assessments administered. The following data will be collected at enrollment:

- Demographics
- Medical & surgical history

Medtronic Business Restricted

- PD history
- Concomitant medications
- Columbia Suicide Severity Rating Scale (C-SSRS) (screening)

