If only one hemisphere has LFP Alpha - Beta signal $\geq 1.2\mu\text{Vp}$ when setting up Single Threshold mode, the clinician should configure adaptive therapy in only that hemisphere with LFP Alpha - Beta signal $\geq 1.2\mu\text{Vp}$.

- cDBS should be setup in the hemisphere with LFP Alpha - Beta signal $< 1.2\mu\text{Vp}$ (set to Passive Sensing, if possible).
- Note: that the stimulation electrode(s) or cathode(s) in the hemisphere set to cDBS is not constrained to a sensing configuration.

If one aDBS mode cannot be set up, the subject should continue with the study using only the mode that can be set up and the subject will not be randomized.

If neither aDBS mode can be set up, the subject will be exited from the study following the process in [Section 9.19](#), including uploading the programming session, with BrainSense data included in the JSON session data report, to Medtronic via CDU. No further study-related procedures will be completed, and subjects will be followed according to the center's standard procedures.

Following each aDBS setup visit day, the programming sessions, with BrainSense data included in the JSON session data report, will be uploaded to Medtronic via CDU.

Once aDBS is set up, and prior to the subject leaving the study center On aDBS, the subject's commercially available Patient Programmer System will be replaced with an investigational-marked Patient Programmer System, and the subject will be given the investigational patient labeling. The

Medtronic Business Restricted

clinician or appropriately delegated study personnel will assist the subject to pair the investigational Patient Programmer System with the INS.

Subjects will be instructed on how to pause aDBS any time they feel like the therapy is not working for them by selecting Pause Adaptive Therapy. This Pause Adaptive Therapy (amplitude last delivered in that group prior to starting aDBS therapy (i.e. the suspend amplitude)) is defined by the clinician as part of the aDBS setup process, following the streaming transition schemes testing and prior to starting adaptive therapy. Subjects will notify the investigator when they pause aDBS to assess the scenario and need for any adjustments.

If the visit occurs over 2 days, the clinician may program the subject to one aDBS mode between visit day 1 and visit day 2.

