9.16. Assessment of Safety

Subjects will be assessed for all potential Adverse Events and device deficiencies, as applicable, at each study visit from the time the study informed consent form is signed until discontinuation from the study. Safety data collected for this study will include all device deficiencies, and all reportable AEs. Refer to [Section 11: Adverse Events and Device Deficiencies](#).

⁸ Jacobson B, et al. “The Voice Handicap Index (VHI): Development and Validation.” American Journal of Speech-Language Pathology. Vol 6. No 3. August 1997. P. 66-70.

Medtronic Business Restricted

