11.1. Adverse Events

AE definitions are provided in [Table 7](#). All AE information will be collected throughout the study duration, starting at the time of signing the IC.

Reporting of these events to Medtronic will occur on an AE eCRF. Each event must be reported separately. Documented pre-existing conditions are not considered AEs unless the nature or severity of the condition has worsened.

In all geographies, UAE, listed in [Table 7](#), need not be reported unless the adverse event worsens or is present outside the stated timeframe post-system modification.

For AEs that require immediate reporting (see [Table 9](#)), initial reporting may be done by phone, email, or on the CRF completing as much information as possible. The completed AE CRF must be submitted to Medtronic as soon as possible.

Any medication/treatment associated with the treatment of an AE must be reported.

All non-subject AEs will be collected throughout the study duration

Subject deaths are also required to be reported. Refer to [Section 11.6](#) for Subject Death collection and reporting requirements.

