7.10 Safety Evaluation

The safety assessment is to characterize:

- Stimulation-related adverse events during the aDBS evaluation and the cDBS baseline phases.
- Serious adverse events, adverse events, and device deficiencies throughout the study.

Stimulation-related adverse events will be summarized during the cDBS Baseline and aDBS Evaluation Phases for all subjects, with tabulations individualized by aDBS mode in the Primary Cohort, by target site in the Primary Cohort, by lead type in the Primary Cohort, and the Directional Stimulation Cohort (DSAT analysis set). Summarized results from the Directional Stimulation Cohort will be provided as supporting analyses to the Primary Cohort results. In the Primary Cohort, if statistical comparisons of poolability across mode, lead type, and target site are accepted, overall tabulations will be provided as appropriate. To test for a difference in safety by target site (STN/GPi) and lead type, Fisher's exact test will be computed testing for differences between target sites and between lead type in the proportion

of subjects with a stimulation-related adverse event during the aDBS Evaluation Phase using data from both periods. [REDACTED]

[REDACTED]

[REDACTED]

[REDACTED]

A repeated measures logistic regression will be used to test for a difference between aDBS modes in the proportion of subjects with stimulation-related adverse events in the randomized subjects who enter the aDBS evaluation phase in the Primary Cohort. [REDACTED]

[REDACTED]

[REDACTED]

[REDACTED]

[REDACTED]

[REDACTED]

P-values >0.1 will be deemed as supporting the assumption of no target site, lead type, or mode effect, respectively, and the data will be considered poolable across the respective variable. If the p-value approaches statistical significance (defined as ≤ 0.1),¹ safety summaries will not be provided as a combined summary for that variable.

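### Suicidality has no structured follow-up on cDBS: after Enrollment the C-SSRS is next given at the aDBS Evaluation visits, and the SAP plans no summary of it

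*Protocol*

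**What the plan says.** **C-SSRS schedule.** Protocol 9.7.1 and Table 3 place the screening form at Enrollment. The follow-up row of Table 3 has two marks, and the visit lists in 9.10.1 and 9.10.2 put them at aDBS Evaluation Visits 1 and 2. The lists for LFP Screening (9.8.1), cDBS Baseline (9.8.3), aDBS Setup (9.9.1) and Randomization (9.9.3) do not contain the scale.

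**General adverse events.** Protocol 9.16: "Subjects will be assessed for all potential Adverse Events and device deficiencies, as applicable, at each study visit". Protocol 11.1: "All AE information will be collected throughout the study duration, starting at the time of signing the IC".

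**Unscheduled visits.** Protocol 9.13 requires a record, including an adverse event and device deficiency assessment, for any visit "for aDBS programming adjustment/optimization (including resuming aDBS if it was unintentionally turned off) or for an Adverse Event". Protocol 9.7.1 allows clinically necessary changes to cDBS settings, but 9.13 does not name a visit made for that purpose alone. Protocol 9.9.1 adds a contact that exists only under aDBS: "Subjects will notify the investigator when they pause aDBS to assess the scenario and need for any adjustments".

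**Analysis.** SAP 7.10: "Stimulation-related adverse events will be summarized during the cDBS Baseline and aDBS Evaluation Phases for all subjects". Neither SAP 7.10 nor Protocol 13.6 mentions the C-SSRS, and the available SAP text does not mention it elsewhere.

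**The concern.** SAP 7.10 summarizes cDBS Baseline and aDBS Evaluation as the two phases of interest for stimulation-related harm. Such a display is easiest to read when harm is looked for in the same way in both. For the C-SSRS it is not. The cDBS Baseline visit repeats most of the instruments used at the Evaluation visits (PDQ-39, EQ-5D-5L, VHI, PDSS-2, MDS-UPDRS), but not this one, and no reason is given.

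Two things are at stake. A positive item at Visit 1 may be new under aDBS or may have begun earlier, and no cDBS follow-up value exists to help tell the two apart. The instrument also has no planned output, so findings on it could go unreported or be reported ad hoc.

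The wording of 9.13 raises a smaller issue of the same kind: contacts for aDBS programming always carry an adverse event check, whereas purely cDBS programming contacts are not named.

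**Working it through.** **The plan's own safety figure.** The documents give no figure for the timing of the C-SSRS. Their one safety calculation (Protocol 13.2.4; SAP 6) says that 30 subjects give at least 95% probability of seeing an event with a true rate of 10% at least once. For a single event type, 1 − 0.9^30 = 0.9576, so the figure is reproduced. It does not depend on the point made here.

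**Visit windows (Protocol Table 4), minimum to maximum days:**

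| Step | Min | Max |
|---|---|---|
| Enrollment to LFP Screening | 1 | 45 |
| LFP Screening to cDBS Baseline | 30 | 45 |
| cDBS Baseline to aDBS Setup | 1 | 45 |
| aDBS Setup to Day 0 (Adjustment) | 0 | 60 |
| Day 0 to Evaluation Visit 1 | 30 | 45 |

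**Sums.**
- Enrollment to Visit 1, that is, screening form to first follow-up form: 1 + 30 + 1 + 0 + 30 = 62 days; 45 + 45 + 45 + 60 + 45 = 240 days.
- Part before Day 0: 1 + 30 + 1 + 0 = 32; 45 + 45 + 45 + 60 = 195.
- Part before the Adjustment period: 1 + 30 + 1 = 32; 45 + 45 + 45 = 135. The difference, 195 − 135 = 60 days, may be spent at home on aDBS (9.9.1, 9.9.2). If Setup takes two days, the subject may also be on aDBS between them.

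**Effect of adding the form at cDBS Baseline.**
- Enrollment to cDBS Baseline: 1 + 30 = 31 to 45 + 45 = 90 days, so the new form would close the cDBS Baseline Phase.
- cDBS Baseline to Visit 1: 1 + 0 + 30 = 31 to 45 + 60 + 45 = 150 days, of which 1 to 105 (45 + 60) precede Day 0. The Setup and Adjustment stretch therefore remains, and the SAP table needs onset dates as well.

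**Scheduled assessments, from the visit lists:**

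| | Before aDBS Evaluation | aDBS Evaluation |
|---|---|---|
| Adverse event assessment | 5 (Enrollment, LFP Screening, cDBS Baseline, Setup, Randomization), the first 4 at visits attended on cDBS | 1 or 2 |
| C-SSRS screening | 1 | 0 |
| C-SSRS follow-up | 0 | 1 or 2 |

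The imbalance lies in the C-SSRS rows. The adverse event row shows none against cDBS.

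**Section 9.13.** A visit prompted by an adverse event is covered in either mode, because that limb of the sentence is not restricted. The uncovered case is a cDBS programming visit with no adverse event as its reason. The documents give no count or rate for such visits.

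**The case against.** The strongest reply is that harm is sought throughout. Adverse events are reported from consent, assessed at each of the five listed visits before Evaluation, and carry a date of event as a minimum field (Protocol 11.5). Related events go to an independent committee (11.5.1, 12.2). To count in the SAP 7.10 comparison, ideation would have to be reported as an adverse event and judged stimulation-related. The safety aim is to characterize, and no test compares aDBS with cDBS. Emotional well-being, anxiety/depression and rater-assessed MDS-UPDRS Part IA are collected at both cDBS Baseline and Evaluation. The protocol expects cDBS settings to be stable, so purely cDBS programming visits should be few. Pause notification concerns a function that cDBS does not have.

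Most of this stands, and it rules out several stronger readings that a reader might infer:

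- *Harm is elicited under aDBS but not under cDBS, or other events are first recorded at aDBS Evaluation.* Protocol 9.16, 11.1 and the visit lists contradict both.
- *A suicidality signal could not be placed in time.* An adverse event report carries a date.
- *The pre-Day 0 share of the gap measures bias.* That share runs from 32/(32 + 45) = 42% to 195/(195 + 30) = 87%, but it assumes that the form looks back to Enrollment, which the documents do not say, and its upper end counts up to 60 days of possible aDBS use.

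What the reply leaves open is narrower. The date field belongs to adverse event reports, and neither document says that a positive C-SSRS item becomes one. Protocol 11.4 says that worsening quality-of-life scores are not adverse events, so the shared questionnaires do not fill the gap. Routine adverse event inquiry is also not the same as a structured suicidality scale.

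**Conclusion.** The point holds in a limited form. Structured suicidality follow-up exists only at aDBS Evaluation visits, 62 to 240 days after the screening form, with 32 to 195 of those days before Day 0 and up to 60 of them possibly aDBS Adjustment. These figures assume visits within the Table 4 windows; Protocol 9.3 retains late visits.

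That ideation from before Day 0 would first be picked up by the scale at an aDBS visit is a possibility and depends on the unstated recall period. If recall reaches back to the previous form, Visit 1 mixes cDBS, Setup, Adjustment and Evaluation time. If it is short, the follow-up form never covers the cDBS Baseline Phase. Under either assumption there is no cDBS follow-up value.

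The 9.13 gap is real but minor and cannot be sized. No endpoint, sample size, power or alpha is affected. This is an inexpensive improvement to the safety comparison and does not amount to a flaw in the general collection of adverse events.

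**What to change.** 1. In Protocol 9.8.3 and Table 3, add the existing C-SSRS follow-up form to the cDBS Baseline visit.
2. In Protocol 9.13, change the programming trigger so that it covers any DBS programming adjustment, cDBS or aDBS. Leave the adverse event limb as it is.
3. In SAP 7.10, add a descriptive C-SSRS table by phase. Assign each positive item to a phase by its onset date. For subjects already past Baseline, show items of unknown onset in a separate row and do not count them under aDBS.

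The cost is a few minutes of subject time at one existing visit, one phrase in 9.13 and one extra table. The third step is useful even for subjects whose Baseline visit has passed.
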